5.4 Subject Disposition

The numbers of subjects enrolled, treated, discontinued from treatment (by reason) will be presented by treatment group.

A summary of subject disposition will be provided for all subjects. Descriptive summaries of subject disposition, reason for discontinuation, and analyses populations will be provided by treatment group. The data will also be presented in subject data listings.

5.6 Study Drug Exposure and Compliance

Number of applications, days of exposure (i.e. duration of treatment), and compliance rate will be summarized by treatment group using descriptive statistics. For each subject, the duration of treatment (days) will be calculated using the following formula:

(Date of last application of study medication) - (Date of first application of study medication) + 1.

Medication compliance rate (%) will be calculated for each subject as follows:

(Total number of applications used) / (Expected number of applications) *100%.

[figure not shown]
5.7 Efficacy Analyses

5.7.1 Primary Endpoint

The primary efficacy endpoint is mean change from baseline in IOP of both eyes at four time points, i.e., at approximately 8:00 a.m. (hour 0; before the morning drop) and approximately 10:00 a.m. (hour 2) at Day 14 (Week 2) and Day 42 (Week 6) visits. The IOP at hour 8:00 a.m. (hour 0) on day 0 will serve as baseline for IOP at hour 8:00 a.m. for Day 14 and Day 42, while IOP at hour 10:00 a.m. (hour 2) on day 0 will serve as baseline for IOP at hour 10:00 a.m. for Day 14 and Day 42. Mean change from baseline to Day X Hour Y in IOP for each subject will be derived as the average difference IOP of (Day X Hour Y – Day 0 Hour Y) from the left and right eyes, where X = 14, 42 and Y = 0, 2.

For test formulation to be considered bioequivalent to the reference formulation, the limits of each two-sided 95% confidence interval of the treatment difference (test – reference) for mean change from baseline IOP of both eyes at all four follow-up points (i.e., at approximately 8:00 a.m. (hour 0; before the morning drop) and 10:00 a.m. (hour 2) at the Day 14 (week 2) and Day 42 (week 6) visits must be within ± 1.5 mm Hg using the PP population and within ± 1.0 mm Hg using the PP population for the majority of time points measured.

[REDACTED]

[REDACTED]

[REDACTED]

[REDACTED]

[REDACTED]

[REDACTED]

[REDACTED]

[REDACTED]

5.8 Safety Variables and Analyses

All safety data will be listed and tabulated. The analysis will be performed on the safety population. Safety parameters include adverse events, vital signs, physical examination findings.

Adverse Events

Adverse events (AEs) will be coded in MedDRA, version 22.0. Treatment-Emergent Adverse Event (TEAE) is defined as any AE occurs on or after application of the first dose of study drug. Number and percent of subjects reporting TEAEs will be tabulated by treatment group. Summaries of TEAEs will be presented by body system and preferred term, and further by severity and relationship to study medication. Most common TEAEs will include those reported by 5% or more subjects for any treatment group will be summarized by preferred term. In the summaries of incidence rates (frequencies and percentages), severity and relationship to study drug, subjects who report more than one event that are mapped to the same preferred term will be counted only once under the strongest severity and relationship, accordingly. The difference between Test and Reference treatments with regard to severity and frequency of their adverse events will be statistically evaluated using Chi-Square or Fisher's exact test to compare the proportions of subjects of the two treatment groups who report any TEAE.

Treatment-Emergent Serious Adverse Events (TESAEs) will be discussed within the clinical study report. TEAEs, TESAEs and TEAEs that led to study treatment interrupted temporarily or study treatment discontinued permanently will be presented in data listings.

All information pertaining to adverse events will be listed by subject, detailing verbatim term given by the investigator, preferred term, system organ class, start date, stop date, severity, outcome, action taken and formula relatedness. Separate listings will be created for Serious TEAEs and TEAEs leading to study formula discontinuation.

Concomitant Medications and Vital Signs

Concomitant medications will be coded using the WHO Drug Dictionary, version March 2019, and will be presented in data listings. All vital signs data will be displayed in listings.

6 Appendices

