7.2. Definitions

An adverse event (AE) is defined as any untoward medical occurrence in a subject administered a medicinal product and which does not necessarily have to have a causal relationship with this treatment. An adverse event can therefore be any unfavorable and unintended sign (for example, an abnormal laboratory finding), symptom, or disease temporally associated with the use of a medicinal product, whether or not considered related to this medicinal product.

A serious adverse event (SAE) is an adverse event that results in any of the following outcomes:

- death
- life-threatening event (i.e., the subject was, in the opinion of the investigator, at immediate risk of death from the event as it occurred. It does not include an event that, had it occurred in a more severe form, might have caused death
- o requires in-subject hospitalization or prolongs hospitalization
- a persistent or significant disability/incapacity or substantial disruption of the ability to conduct normal life functions
- congenital anomaly/birth defect

 Other adverse events that may be considered serious based upon appropriate medical judgment, may jeopardize the subject and may require medical or surgical intervention to prevent one of the outcomes listed above.

Immediately Reportable Adverse Events (IRAE): Any serious AE or any AE that necessitates discontinuation of study medication, including pregnancy.

Unexpected Adverse Event: An unexpected event is any adverse drug experience, the specificity or severity of which is not consistent with the current approved product labeling (package insert) for the study medication, the Investigator's Brochure, or as described in the clinical protocol and consent materials.

Intensity of Adverse Events:

The maximum intensity of an AE during a day should be recorded on the CRF. If the intensity of an AE changes over a number of days, then separate entries should be made having distinct onset dates for the changes in severity.

Mild - AEs are usually transient, requiring no special treatment, and do not interfere with subject's daily activities.

Moderate - AEs typically introduce a low level of inconvenience or concern to the subject and may interfere with daily activities but are usually ameliorated by simple therapeutic measures.

Severe - AEs interrupt a subject's usual daily activity and traditionally require systemic drug therapy or other treatment.

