7.3. Eliciting and Reporting of Adverse Events

All adverse events (as defined in Section 7.2), either observed by the investigator or one of his/her medical collaborators, or reported by the participant spontaneously, or in response to direct questioning, will be reported and documented in the source document and the study reporting forms. When reporting an adverse event, the investigator must assign a severity grade to each event and declare an opinion on the relatedness of the event to the study medication or procedure. Serious or unexpected adverse events must be reported within 24 hours of when the investigator first learns of the occurrence of the event.

Adverse events will be documented in the source document and recorded in a timely manner on the eCRFs. Adverse events that are identified at the last assessment visit (or the early termination visit) must be recorded on the AE eCRF with the status of the AE noted.

Adverse event reporting begins from the signing of informed consent. Adverse events should be followed until resolved or 30 days after the final study treatment. In any case, serious adverse events that are not resolved or considered to be chronic within 30 days of the final study treatment must be followed by the investigator until they become resolved or are considered to be chronic (stabilized for at least 30 days). All events that are ongoing at this time will be recorded as ongoing on the eCRF.

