3.1 Study Design

For the purpose of exploring the above objectives, the study will be conducted as a double-masked, randomized, multi-center, active-controlled, parallel-group study.

Each subject will be randomly assigned to one of the following treatment groups [REDACTED]:

- (1) Test: Brinzolamide Ophthalmic Suspension, 1%, Perrigo Pharma International DAC, Ireland, [REDACTED]
- (2) Reference: Azopt® (brinzolamide ophthalmic suspension), 1%, manufactured by Novartis Pharmaceuticals Corporation.

The study consists of a run-in phase and a six-week treatment (42 ± 4 days) period.

At Baseline/Visit 2, eligible subjects who meet all inclusion criteria and do not meet any exclusion criteria will be randomized [REDACTED] to either the test or reference product for the 6-week treatment period. Subjects will apply one drop of either test product or reference product in both eyes three times daily at approximately 08:00 am, 04:00 pm and 10:00 pm for six weeks (42 ± 4 days).

Subjects will come to the study site for clinical evaluations Visit 1/Screening, Visit 2/Day 0 (Baseline), Visit 3/Week 2/Day 14 (± 4 days), and Visit 4/Week 6/Day 42 (± 4 days) (End of Study) or at early discontinuation. Safety will be assessed by monitoring adverse events at each visit.

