6.1 Handling of Missing or Incomplete Dates for Adverse Events and Concomitant Medications

Adverse Events

Handling of partial dates is only considered for the start date. An adverse event with a partial start date is considered treatment emergent if:

- only the day is missing and the start month/year is the same or after the month/year of the first dose
- the day and month are missing and the start year is the same or greater than the year of

the first dose date

- the start date is completely missing

Concomitant Medications

Handling of partial dates is only considered for the stop date. A medication with a partial stop date is considered concomitant if:

- only the day is missing and the stop month/year is the same or after the month/year of the first dose
- the day and month are missing and the stop year is the same or greater than the year of the first dose date
- the stop date is completely missing or the medication is ongoing

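### A run-in adverse event that eases after the first dose is counted as treatment-emergent, because the protocol gives the change in intensity a new onset date and the SAP classifies by start date alone

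*SAP*

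**What the plan says.** Four rules in the two documents meet here.

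- **Collection starts before dosing.** Protocol 7.3: "Adverse event reporting begins from the signing of informed consent". SAP 3.1: "The study consists of a run-in phase and a six-week treatment (42 ± 4 days) period". AEs that began before the first randomised dose can therefore be on file.
- **A change in intensity creates a new entry.** Protocol 7.2 first limits what is recorded within a day: "The maximum intensity of an AE during a day should be recorded on the CRF". For an AE whose intensity changes over several days, it says "separate entries should be made having distinct onset dates for the changes in severity". The direction of the change is not restricted.
- **Treatment emergence is decided by timing alone.** SAP 5.8: "Treatment-Emergent Adverse Event (TEAE) is defined as any AE occurs on or after application of the first dose of study drug". SAP 6.1 shows that the start date is the operative date, since its rule for incomplete dates opens "An adverse event with a partial start date is considered treatment emergent if" and goes on to compare the start date with the first dose.
- **Repeated events are collapsed within a preferred term.** SAP 5.8: "subjects who report more than one event that are mapped to the same preferred term will be counted only once under the strongest severity and" (the sentence treats causal attribution in the same way).

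SAP 5.8 then compares the arms by a chi-square or Fisher's exact test on the proportion of subjects with any TEAE. The tables by preferred term, severity, relationship and 5% frequency also count TEAEs.

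**The concern.** Each rule is workable alone. Together they misclassify one kind of history: an AE that began in run-in, was still present at the first dose, and then improved. The improvement creates an entry dated after dosing, and that entry meets the TEAE definition. Had the AE not improved, there would be no such entry and no TEAE. A rule that counts improvement as treatment-emergent, but not persistence, is unlikely to be what was meant.

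At stake is the accuracy of the safety tabulation. TEAE rates are slightly inflated, the severity and relationship tables gain entries that are not treatment-emergent, and a real difference between arms in the any-TEAE proportion is diluted by background common to both.

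A secondary gap runs the other way. A pre-dose AE that becomes serious after dosing without a change of intensity grade keeps its pre-dose start date, so it would not carry the Serious TEAE label used for one of the SAP 5.8 listings.

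**Working it through.** The documents state no figure on this point, so there is none to reproduce. The check has two parts.

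**1. Tracing the rules.** Days are counted from first dose as in SAP 5.1. The comparison rule is: new, or worse than the worst pre-dose intensity.

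| History | Post-dose entry under Protocol 7.2 | TEAE under SAP 5.8 and 6.1 | TEAE if new or worsened |
|---|---|---|---|
| A. Moderate Day -10, mild from Day 3 | mild, onset Day 3 | yes (mild) | no |
| B. Mild Day -10, moderate from Day 3 | moderate, onset Day 3 | yes | yes |
| C. Mild Day -10, unchanged | none | no | no |
| D. New mild event Day 5 | mild, onset Day 5 | yes | yes |

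Only history A is misclassified. B shows that the split entry already captures worsening. The collapsing rule does not rescue A: if the Day 3 entry is the subject's only post-dose entry for that term, there is nothing to collapse it into. SAP 6.1 does not help, because these dates are complete.

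The affected set is narrow. Protocol 7.2 has three grades, so a mild run-in AE has no lower grade to fall to, and if it resolves it ends without a new entry. The error needs a moderate or severe run-in AE that persists past first dose and then falls to a lower grade. To change the any-TEAE test, the subject must also have no true TEAE.

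**2. Size, on assumed inputs.** Let p be the true any-TEAE proportion and q the share of subjects without a true TEAE who have an easing run-in AE, equal in both arms.

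- Observed proportion = p + (1 - p)q.
- Observed difference = (p2 - p1)(1 - q).

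Assumed, not from the documents: p1 = 20%, p2 = 30%, q from 0 to 10%, and 150, 200 or 300 subjects per arm (the planned number is not visible). Two-sided alpha of 0.05 is from Protocol 8.1.

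For q = 5%: 0.20 + 0.80 × 0.05 = 0.240 and 0.30 + 0.70 × 0.05 = 0.335, a difference of 0.095.

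Power is the normal approximation Φ[(d - 1.96·SE0)/SE1], with d the observed difference, SE0 the pooled standard error and SE1 the unpooled one. At 200 per arm and q = 5%, SE0 = √(0.2875 × 0.7125 × 2/200) = 0.0453 and SE1 = √[(0.240 × 0.760 + 0.335 × 0.665)/200] = 0.0450. Power is 55.6%.

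| q | Observed rates | Difference | Power, 150/arm | 200/arm | 300/arm |
|---|---|---|---|---|---|
| 0 | 20.0% v 30.0% | 10.0 points | 51.6% | 63.8% | 80.9% |
| 1% | 20.8% v 30.7% | 9.9 | 50.0% | 62.0% | 79.3% |
| 5% | 24.0% v 33.5% | 9.5 | 44.3% | 55.6% | 73.0% |
| 10% | 28.0% v 37.0% | 9.0 | 38.3% | 48.5% | 65.4% |

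The loss of power exceeds the shrinkage of the difference because the added background also raises the variance. When the true rates are equal, both rise equally and no false difference arises on average.

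**The case against.** **The SAP's wording is open.** It speaks of an AE that occurs after first dose and never says that each eCRF entry is an AE. The protocol speaks of one AE with several entries, and says they should be made, not must. A programmer could treat the episode as the AE and use its first onset. That is a fair reading, and nothing visible excludes it. But it would also drop history B, a run-in AE that worsens on treatment. Either reading leaves one class of event wrongly placed unless the definition is completed.

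**The size may be negligible.** This stands. The documents give no run-in AE rate, and the grade restriction makes the 5% and 10% rows look high. Ratios can also mislead: with assumed rates of 20% and 10%, q = 5% gives 24.0% and 14.5%, so the ratio falls from 2.0 to 1.66, yet the difference falls only from 10.0 to 9.5 points. The SAP compares proportions.

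**Stronger readings that the documents do not support.**

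- A reader might infer that the rule tilts the trial towards its desired conclusion. Bioequivalence is decided only by the confidence intervals for intraocular pressure (Protocol 8.5, SAP 5.7.1). No visible safety criterion depends on the any-TEAE test, and because run-in AEs precede randomisation, neither arm is favoured systematically.
- A reader might infer that serious events are lost. SAP 5.8 lists all AE information by subject, Listing 16.2.7.3 is titled for serious adverse events without restriction to treatment-emergent ones, and Protocol 7.6 requires reporting of any serious event after study entry. Only the label is missed.
- A reader might infer that every change of intensity creates a false TEAE. Within-day changes do not create entries, and worsening is correctly counted.

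**Text is missing.** Run-in details, eCRF specifications and table shells are not visible, so a linking rule elsewhere cannot be ruled out. SAP 5.8 and 6.1 show no redaction at this point and refer to no such rule.

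**Conclusion.** The point holds in a limited form. As written, Protocol 7.2 with SAP 5.8 and 6.1 counts as a TEAE a moderate or severe run-in AE that eases to a lower grade after first dose. It does not count the same AE left unchanged. This is a misclassification by stated rules, not merely a missing detail, though it rests on taking each dated entry as an AE, as the start-date rule in SAP 6.1 suggests.

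The effect is probably small: a slight inflation of TEAE rates in both arms and a slight dilution of the any-TEAE comparison, by the factor (1 - q). Its true size cannot be had from the documents. The efficacy conclusion is unaffected. The missed Serious TEAE label is a secondary matter. The correction is still worth making, because the any-TEAE comparison is the formal between-group safety test in the plan.

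**What to change.** Amend SAP 5.8 before database lock:

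1. Define a TEAE as an AE that first starts on or after the first dose of randomised study drug, or that started earlier and, on or after that dose, exceeds its worst pre-dose intensity or becomes serious. Naming the randomised drug matters because the title of Listing 16.2.5.1 mentions dispensing at Visit 1 as well as Visit 2.
2. State that an entry continuing a pre-dose AE at equal or lower intensity is not a TEAE, unless the event becomes serious. An event that only returns to a level already seen in run-in is then not counted.
3. Link the split entries of one episode in programming, by verbatim term and abutting dates.

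No new eCRF field is needed, Protocol 7.2 can stay as it is, and visits and subject procedures do not change. The cost is a few sentences in the SAP, a small amount of extra programming, and a review of the linked entries, which should be done before unmasking.

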6.1 Handling of Missing or Incomplete Dates for Adverse Events and Concomitant Medications

Adverse Events

Handling of partial dates is only considered for the start date. An adverse event with a partial start date is considered treatment emergent if:

- only the day is missing and the start month/year is the same or after the month/year of the first dose
- the day and month are missing and the start year is the same or greater than the year of

the first dose date

- the start date is completely missing

Concomitant Medications

Handling of partial dates is only considered for the stop date. A medication with a partial stop date is considered concomitant if:

- only the day is missing and the stop month/year is the same or after the month/year of the first dose
- the day and month are missing and the stop year is the same or greater than the year of the first dose date
- the stop date is completely missing or the medication is ongoing

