Study	To demonstrate b	ioequivalence of brinzolamide ophthalmic suspension 1% (Perrigo
Objectives	Pharma Internation	onal DAC) to Azopt® (brinzolamide ophthalmic suspension) 1%
	(Novartis Pharmac	ceutical Corporation) by comparing their efficacy and safety in the
	treatment of sub	ojects with Primary Open Angle Glaucoma (POAG) or Ocular
	Hypertension (OH) in both eyes.
Study Design	Double-masked,	randomized, multi-center, active-controlled, parallel-group,
	 	udy with clinical endpoint.
Study		subjects will be enrolled to obtain
Population		per protocol subjects. All efforts will be made so that the study
	population will co	nsist of subjects with light colored iris and dark colored iris similar
	in proportion to the	ne U. S. population.
Dosing	The study consists	of a six-week treatment (42 ± 4 days) period.
	l	, eligible subjects will be randomized in a double-masked manner,
		ther the test product or reference product. Subjects will apply one
		t product or reference product in both eyes three times daily at
	· · · ·	00 am, 04:00 pm and 10:00 pm for six weeks (42 ± 4 days)
Study Visits		s will be performed at:
	1. Visit 1/Scre	_
	2. Visit 2/Day	,
	-	ek 2/Day 14 (±4 days)
	4. Visit 4/We	ek 6/Day 42 (±4 days) (End of Study)

Title	A Multi-Center, Randomized, Double-Masked, Active Controlled, Parallel Group Bioequivalence Study with Clinical Endpoint Comparing Brinzolamide Ophthalmic Suspension 1% of Perrigo Pharma International DAC to Azopt® (brinzolamide ophthalmic suspension) 1% of Novartis Pharmaceuticals Corporation in the Treatment of Primary Open Angle Glaucoma or Ocular Hypertension in Both Eyes
Evaluations	 Intraocular pressure Vital signs Adverse events
Primary	The primary efficacy endpoint is mean change from baseline in IOP of both eyes at
Endpoint	four time points, i.e., at approximately 8:00 a.m. (hour 0; before the morning drop)
	and approximately 10:00 a.m. (hour 2) on Day 14 (Week 2) and Day 42 (Week 6)
	visits.
Safety	The incidence of all adverse events reported during the study will be summarized by
	treatment group. Test and reference product will be compared for safety by
	analyzing nature, severity and frequency of treatment emergent adverse events.

List of Abbreviations

AE	Adverse Event
ANOVA	Analysis of Variance
СМН	Cochran–Mantel–Haenszel test
CAI	Carbonic Anhydrous Inhibitor
CRA	Clinical Research Associate
CRO	Clinical Research Organization
dB	Decibel
eCRF	Electronic Case Report Form
EDC	Electronic Data Capture

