2.2. Safety

Safety of the test and reference products will be compared by evaluating the nature, severity and frequency of their adverse event profiles. All adverse events that occur during the study will be recorded whether or not they are considered to be related to the study medication. The report of AEs should include date of onset, description of the AE, severity, relation to study medication, action taken, outcome and date of resolution. Comparisons between the treatment groups will be made by tabulating the frequency of subjects with one or more adverse events (classified into MedDRA terms) during the study. Pearson's Chi-Square test or Fisher's Exact test, whichever is most appropriate, will be used to compare the proportion of subjects in each treatment group with any adverse event. The adverse events reported by at least five percent of the subjects in any treatment group will be summarized descriptively.

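### SAP 6.1 counts an adverse event with an incomplete start date as treatment-emergent even when its recorded stop date is before the first dose

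*SAP*

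**What the plan says.** SAP 5.8 gives the definition: "Treatment-Emergent Adverse Event (TEAE) is defined as any AE occurs on or after application of the first dose of study drug".

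SAP 6.1 then deals with incomplete AE dates. It opens with "Handling of partial dates is only considered for the start date" and lists three situations in which the event is treated as treatment-emergent:

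1. "only the day is missing and the start month/year is the same or after the month/year of the first dose";
2. "the day and month are missing and the start year is the same or greater than the year of" the first dose;
3. "the start date is completely missing".

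None of the three refers to the stop date, and no other readable part of either document adds an exception.

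The stop date is planned data. Protocol 2.2 includes "action taken, outcome and date of resolution" among the items of every AE report, and SAP 5.8 has the AE listing show "start date, stop date, severity, outcome, action taken and formula relatedness". For concomitant medications, SAP 6.1 itself uses the stop date to classify.

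**The concern.** An event that is known to have ended before first dose cannot be a TEAE under SAP 5.8, whatever is unknown about its start. SAP 6.1, followed literally, makes it one.

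Such events can be on the database. Protocol 7.3 starts AE reporting at consent, and SAP 3.1 describes a run-in phase before randomization at Visit 2. An AE can therefore begin and resolve before any study drug is used.

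Two outputs are exposed. The first is the set of five TEAE tables (14.3.2.1 to 14.3.2.5). The second is the SAP 5.8 chi-square or Fisher comparison of subjects with any TEAE. The protocol synopsis also bases the safety comparison on TEAEs, by "analyzing nature, severity and frequency of treatment emergent adverse events". Protocol 2.2 and 8.6 instead word the test as any adverse event. Under that wording the classification would not change the test, though it would still change the TEAE tables.

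**Working it through.** **Inputs**

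- TEAE definition: SAP 5.8.
- Three rules for incomplete start dates: SAP 6.1.
- Study Day before first treatment = date of finding − date of first treatment: SAP 5.1.
- First dose on 20 June: assumed, for illustration.
- TEAE rates and misclassified fraction in step 3: assumed. The documents give neither.

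The plan has no figure of its own to reproduce on this point.

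**Step 1. Apply SAP 6.1 to events that all stopped before first dose**

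| Start date as recorded | Stop date | Study Day of stop | SAP 6.1 | SAP 5.8 |
|---|---|---|---|---|
| June, day missing | 10 June | 10 − 20 = −10 | TEAE | not a TEAE |
| same year, day and month missing | 31 May | −20 | TEAE | not a TEAE |
| completely missing | 31 May | −20 | TEAE | not a TEAE |
| May, day missing | 10 June | −10 | not a TEAE | not a TEAE |
| previous year, day and month missing | 10 June | −10 | not a TEAE | not a TEAE |
| 5 June (complete) | 10 June | −10 | rule not needed | not a TEAE |

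The two sections disagree in the first three rows, one for each rule. They agree when the known part of the start date already falls before first dose and when the start date is complete. A start month after that of first dose cannot come with an earlier stop date, so it raises no conflict.

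**Step 2. How wide the gap is**

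For the first rule with this first dose, the pre-dose stop dates within June run from 1 to 19 June. That is 19 dates, from Study Day 1 − 20 = −19 to 19 − 20 = −1, and every one gives a TEAE. All 19 can arise only if consent was on or before 1 June, since AE reporting starts at consent. For the other two rules, every stop date from consent to 19 June gives a TEAE (for the year-only rule, provided consent was in the same year).

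**Step 3. Effect on the any-TEAE comparison**

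Let p be the true proportion with any TEAE in an arm, and f the fraction of TEAE-free subjects falsely counted, taken as equal in both arms. The observed proportion is

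p′ = p + f(1 − p),

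so p₁′ − p₂′ = (1 − f)(p₁ − p₂).

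With p₁ = 0.20 and p₂ = 0.10:

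| f | p₁′ | p₂′ | Difference |
|---|---|---|---|
| 0 | 0.2000 | 0.1000 | 10.0 points |
| 0.005 | 0.2040 | 0.1045 | 9.95 points |
| 0.01 | 0.2080 | 0.1090 | 9.9 points |
| 0.05 | 0.2400 | 0.1450 | 9.5 points |

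The last row is a deliberately high value, included to show that even then the shift is modest.

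**Step 4. Apply the stop-date exception**

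If an AE with a known stop date before first dose is excluded, the first three rows of the step 1 table become non-TEAEs and the other three do not change. SAP 6.1 and 5.8 then agree in all six.

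**The case against.** The best counter-argument is that the two sections can be read together. SAP 5.8 holds the definition, and SAP 6.1 is an appendix meant only to settle timing when a date is unclear. Its opening sentence may mean no more than that partial stop dates are not resolved. On that reading nothing stops a programmer from using a complete stop date, and the definition already answers the question. The reading is possible, but the text does not say it: the three conditions carry no exception, and nothing states that 5.8 overrides them. Two programmers could follow the same SAP and produce different TEAE counts.

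A second argument is rarity. Protocol 2.2 requires the onset date as well as the resolution date, and protocol 11.1 provides for source verification and data queries. The problem needs an incomplete onset date beside a usable resolution date, for an event that began and ended before first dose. This stands and limits the size of the point. Still, SAP 6.1 exists for the dates that remain incomplete after querying, so it should classify those correctly.

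A third is that defaulting to treatment-emergent is the cautious choice. That is sound while timing is in doubt, but a stop date before first dose removes the doubt.

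Finally, the table and listing shells are not in the readable text, so a footnote with a stop-date condition cannot be ruled out. There is no sign of one.

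**Conclusion.** The point holds. As written, each of the three SAP 6.1 conditions can class as treatment-emergent an event that SAP 5.8 excludes. This is a stated rule that gives a wrong answer in a definable set of cases, and not merely a missing detail.

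It is a minor point. The number of affected events cannot be estimated, because the run-in length is not readable and the documents give no count of incomplete dates. Queries should keep that number low. Any effect should be about equal in the two masked arms, and so would slightly dilute a difference between them; the numerical illustration rests on assumed rates. AEs with complete start dates are untouched. Bioequivalence rests on the IOP confidence intervals, which this rule does not enter.

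**What to change.** Add to SAP 6.1, under Adverse Events:

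> An AE with a known stop date before the first dose date is not treatment-emergent, whatever the start-date information; if the stop date is partial, this applies only when its known part places it before first dose.

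Where timing stays in doubt, the existing default of treatment-emergent remains.

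The cost is one SAP sentence and one condition in the TEAE derivation, both to be made before unmasking. No additional data are needed. The one drawback is that the classification of these events then depends on the recorded stop date being correct.
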